13.9 Reporting and Exclusions

All participants will be evaluable for toxicity from the time of their first treatment with eribulin and pembrolizumab. All participants who receive at least one dose of eribulin and pembrolizumab will be included in the toxicity analysis. This includes participants who receive study drug and are ultimately deemed ineligible.

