5.3.2 Pembrolizumab

Pembrolizumab will be administered by trained medical personnel at the investigational site. Treatment compliance will be monitored through documentation of study treatment administration in the participant's medical record.

Pembrolizumab will be administered in the outpatient clinic on Day 1 of each cycle. Pembrolizumab should be prepared and administered as an approximately 30-minute IV infusion per institutional standard, infuse prior to Eribulin

Please refer to the FDA-approved package insert for pembrolizumab for product information and a comprehensive list of adverse events. Pembrolizumab should be prepared and administered per institutional standard. Institutional standard procedures include BSA calculations, body weight assessments and dose calculations/recalculations. Infusion times may be prolonged in participants who experience an infusion reaction as per section 5.9.

Pembrolizumab should be administered prior to eribulin administration. There should be no overlap in timing of the two administrations.

The standard dose of pembrolizumab is 200mg IV.

5.3.3 *Discontinuation of eribulin*

If eribulin is stopped for toxicity, participants are permitted to continue protocol therapy with pembrolizumab alone.

5.3.4 *Discontinuation of pembrolizumab*

If pembrolizumab is stopped for toxicity, participants are permitted to continue protocol therapy with eribulin alone.

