7.3 Expedited Adverse Event Reporting

- 7.3.1 In the event of an unanticipated problem or life-threatening complications treating investigators must immediately notify the Overall PI.
- 7.3.2 Investigators **must** report to the Overall PI any serious adverse event (SAE) that occurs after the initial dose of study treatment, during treatment, or within 30 days of the last dose of treatment on the local institutional SAE form.
- 7.3.3 DF/HCC Expedited Reporting Guidelines

Investigative sites within DF/HCC will report AEs directly to the DFCI Office for Human Research Studies (OHRS) per the DFCI IRB reporting policy.

Table. 5 DF/HCC Reportable AEs

Attribution	DF/HCC Reportable AEs				
	Gr. 2 & 3 AE Expected	Gr. 2 & 3 AE Unexpected	Gr. 4 AE Expected	Gr. 4 AE Unexpected	Gr. 5 AE Expected or Unexpected
Unrelated Unlikely	Not required	Not required	5 calendar days [#]	5 calendar days	24 hours*
Possible Probable Definite	Not required	5 calendar days	5 calendar days [#]	5 calendar days	24 hours*
[#] If listed in protocol as expected and not requiring expedited reporting, event does not need to be reported.					
* For participants enrolled and actively participating in the study or for AEs occurring within 30 days of the last intervention, the AE should be reported within 1 business day of learning of the event.					

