7.6 Expedited Reporting to MERCK

A serious adverse event (SAE) is any adverse event occurring at any dose or during any use of Merck's product that:

- Results in death;
- Is life threatening;
- Results in persistent or significant disability/incapacity;
- Results in or prolongs an existing inpatient hospitalization;
- Is a congenital anomaly/birth defect;
- Is a new cancer (that is not a condition of the study);
- Is associated with an overdose;
- Is another important medical event

Any serious adverse event, or follow up to a serious adverse event, including death due to any cause other than progression of the cancer under study that occurs to any participant from the time the consent is signed through 90 days following cessation of treatment, or the initiation of new anti-cancer therapy, whichever is earlier, whether or not related to Merck product, must be reported within 24 hours to the Sponsor and within 2 working days to Merck Global Safety.

Non-serious Events of Clinical Interest will be forwarded to Merck Global Safety and will be handled in the same manner as SAEs.

Additionally, any serious adverse event, considered by an investigator who is a qualified physician to be related to Merck product that is brought to the attention of the investigator at any time outside of the time period specified in the previous paragraph also must be reported immediately to Merck.

SAE reports and any other relevant safety information are to be forwarded to the Merck Global Safety.

A copy of all 15 Day Reports and Annual Progress Reports is submitted as required by FDA, European Union (EU), Pharmaceutical and Medical Devices agency (PMDA) or other local regulators. Investigators will cross reference this submission according to local regulations to the Merck Investigational Compound Number (IND, CSA, etc.) at the time of submission. Additionally, investigators will submit a copy of these reports to Merck & Co., Inc. at the time of submission to FDA.

All participants with serious adverse events must be followed up for outcome.

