13. STATISTICAL CONSIDERATIONS

13.1 Study Design/Endpoints

We have designed a single stage phase II, three-arm study for the primary endpoint of progression-free rate at 12 weeks. Participants will be stratified among three-arms based upon participant diagnosis. Arm A will consist of leiomyosarcoma participants. Arm B will consist of liposarcoma participants. Arm C will consist of undifferentiated pleomorphic sarcoma/other sarcomas.

The primary endpoint is the 12-week progression-free survival. The progression-free survival is defined as the absence of disease progression at 12 weeks from study enrollment. Participants without stable disease or complete or partial response, with deaths of any cause within 12 weeks, with progression within 12 weeks, or without confirmatory scans at 12 weeks' post baseline evaluation will be counted as failures. We will enroll 19 participants in each arm following a single stage approach.

Toxicity is an important secondary endpoint. With 19 participants in each arm, there is at least 86% probability of observing one or more toxicities with a true rate as low as 10%. With 19 treated participants in each arm, the maximum width of a 90% two-sided confidence interval for any estimated adverse event proportion is $\pm 20\%$.

Progression-free survival (PFS) and overall survival (OS) of participants receiving combination therapy will be described using the method of Kaplan and Meier and 90% confidence intervals for PFS and OS will be reported.

NOTE: With Protocol Version 15MAY2024, further long-term follow-up is being terminated.

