13.2 Sample Size, Accrual Rate and Study Duration

Arm A (Leiomyosarcoma)

We will assess the progression-free rate at 12 weeks (null: 30%, alternative: 60%). We will need to observe at least 9 participants absent of disease progression out of 19 participants to accept the treatment. The overall power for the progression-free rate at 12 weeks is 91% using the exact binomial distribution. The operating characteristics of this design are calculated using a one-sided exact test with 10% type I error.

Arm B (Liposarcoma)

We will assess the progression-free rate at 12 weeks (null: 30%, alternative: 60%). We will need to observe at least 9 participants absent of disease progression out of 19 participants to accept the treatment. The overall power for the progression-free rate at 12 weeks is 91% using the exact binomial distribution. The operating characteristics of this design are calculated using a one-sided exact test with 10% type I error.

Arm C (Undifferentiated Pleomorphic Sarcoma/Other Sarcomas)

We will assess the progression-free rate at 12 weeks (null: 30%, alternative: 60%). We will need to observe at least 9 participants absent of disease progression out of 19 participants to accept the treatment. The overall power for the progression-free rate at 12 weeks is 91% using the exact binomial distribution. The operating characteristics of this design are calculated using a one-sided exact test with 10% type I error. Additionally, response to individual sarcomas histologic subtypes will be reported descriptively.

Table 10. Accrual Targets

Accrual Targets				
Ethnic Category	Sex/Gender			
	Females		Males	Total
Hispanic or Latino	1	+	1	= 2
Not Hispanic or Latino	27	+	28	= 55
Ethnic Category: Total of all participants	28	+	29	= 57
Racial Category				
American Indian or Alaskan Native	1	+	1	= 2
Asian	1	+	1	= 2
Black or African American	1	+	1	= 2
Native Hawaiian or other Pacific Islander	1	+	1	= 2
White	24	+	25	= 49
Racial Category: Total of all participants	28	+	29	= 57

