13.9.1 Evaluation of Toxicity

Toxicity data will be summarized by frequency tables. For the toxicity endpoint, per-treated analysis will be used to include any participant who received the treatment regardless of the eligibility nor the duration or dose of the treatment received. Toxicity rate will be estimated with 95% credible interval.

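### The toxicity population and its interval are each specified in two ways, the toxicity tables have no stated window, and a pooled summary of all 57 participants would add precision

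*Combined protocol and SAP*

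**What the plan says.** **Population.** Section 13.9 of the combined protocol and SAP reads: "All participants who receive at least one dose of eribulin and pembrolizumab will be included in the toxicity analysis". Section 11.1 repeats the sentence, and 11.1.1 starts evaluability for toxicity at first treatment with the two drugs joined by *and*. The next sentence of 13.9 speaks only of study drug. Section 13.9.1 counts any treated participant, whatever the eligibility, duration or dose. On the order of infusion, 5.3.2 says: "Pembrolizumab should be administered prior to eribulin administration".

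**Interval.** Section 13.1 gives the precision: "With 19 treated participants in each arm, the maximum width of a 90% two-sided confidence interval for any estimated adverse event proportion" is ±20%. It also gives at least an 86% chance of seeing one or more toxicities with a true rate of 10%. Section 13.9.1 says: "Toxicity rate will be estimated with 95% credible interval". No prior is given anywhere.

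**Cohorts.** Section 13.1: "We will enroll 19 participants in each arm following a single stage approach". Section 5.1 gives all three arms the same regimen. Objective 1.3.2 is worded for the participant population as a whole. No pooled toxicity summary is described.

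**Windows.** Section 7.3.2 has serious adverse events (SAEs) reported to the Overall PI from the first dose and "within 30 days of the last dose of treatment on the local institutional SAE form". Sections 7.6 and 7.7 have them reported to the Sponsor "from the time the consent is signed through 90 days following cessation of treatment", or to new anti-cancer therapy if that is earlier. Section 7.4 makes the Overall PI the study sponsor. Immune-event follow-up is 90 days in 1.1 and about 100 days in 5.6. The toxicity text in 13.1, 13.9 and 13.9.1 names no window.

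**The concern.** The case that separates the two population rules arises from the protocol's own procedures. Pembrolizumab goes in first, without overlap, and Table 4.8 ends study drug treatment after a Grade 3 or 4 infusion reaction. Such a reaction at Cycle 1 Day 1 can leave a patient who never receives eribulin. Read literally, 13.9 then removes that patient from the toxicity analysis because of a toxicity, and a safety population should never select in that direction.

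The interval matters because 13.1 calls toxicity an important secondary endpoint and supports it with a precision figure that belongs to a different interval from the planned one. A credible interval without a prior cannot be reproduced from the plan.

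The windows matter because 6.2 says immune-related events may appear several months after the last dose. Where the tables stop therefore affects what they show, and the plan does not say where they stop.

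**Working it through.** **1. Reproduce the plan's figures (n = 19 per arm, section 13.1).**
- Chance of at least one event at a true rate of 10%: 1 − 0.90^19 = 1 − 0.135 = 86.5%. Stated: at least 86%.
- Largest half-width of a 90% interval over all possible counts 0 to 19: 20.3% by Clopper-Pearson. The simple normal formula at p = 0.5 gives 1.645 × √(0.25/19) = 18.9%, and Wilson gives 17.6%. The stated ±20% matches the exact 90% interval.

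Both figures are right for what they describe.

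**2. Compare with the interval that 13.9.1 plans.** The prior is not given, so two common ones are assumed.

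| Maximum half-width | n = 19 | n = 57 |
|---|---|---|
| 90% exact (basis of 13.1) | 20.3% | 11.6% |
| 95% credible, uniform prior (assumed) | 20.6% | 12.6% |
| 95% credible, Jeffreys prior (assumed) | 21.1% | 12.7% |
| 95% exact | 23.3% | 13.5% |

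The mismatch at n = 19 is under one percentage point if the interval is credible with one of these priors, and 3 points (23.3 − 20.3) if a 95% exact interval is used.

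**3. Effect of pooling.** n = 3 × 19 = 57, as in Table 10. Chance of at least one event = 1 − (1 − p)^n:

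| True rate p | n = 19 | n = 57 |
|---|---|---|
| 10% | 86.5% | 99.8% |
| 5% | 1 − 0.95^19 = 62.3% | 1 − 0.95^57 = 94.6% |
| 2% | 1 − 0.98^19 = 31.9% | 1 − 0.98^57 = 68.4% |

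If no event of a given type is seen, the upper limit of the two-sided 95% exact interval is 1 − 0.025^(1/19) = 17.6% for one arm and 1 − 0.025^(1/57) = 6.3% pooled. The trial treats the same patients either way. Pooling changes the precision that can be claimed for the regimen, not the events that occur.

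**4. Population rules side by side, for a patient who receives only pembrolizumab.**
- 11.1 and 13.9, first sentence: out if *and* means both drugs; in if it names the regimen.
- 11.1.1 and 13.9, evaluability: same ambiguity.
- 13.9, following sentence: in (study drug).
- 13.9.1: in (any duration or dose).

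How often this arises cannot be computed from the documents. It needs a reaction at the first infusion, before eribulin, in someone who never goes on to eribulin. The documents differ on that last step: Table 4.8 ends study drug treatment, while 5.9 names pembrolizumab only and 5.3.4 permits eribulin alone. Those passages should be reconciled too.

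**5. Windows side by side.**
- 7.3.2: first dose to 30 days after the last dose, to the Overall PI.
- 7.6 and 7.7: consent to 90 days after treatment or new therapy, to the Sponsor, who by 7.4 is the Overall PI.
- Immune events: 90 days (1.1), about 100 days (5.6).
- Toxicity tables: not stated.

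For SAEs, one recipient therefore has two starts and two ends.

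**The case against.** Several stronger readings are tempting, and the documents do not support them.

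- *One-drug patients are excluded.* No section says so. Section 13.9.1, which specifies the toxicity analysis, and the second sentence of 13.9 both point to inclusion. The ambiguity stands; a settled exclusion does not.
- *About 2 of 57 patients are at stake.* A reader might multiply the below-4% infusion-reaction rate in 2.6 by 57 (0.04 × 57 = 2.3). That rate covers all grades and is not limited to the first infusion, so it cannot be applied to the much narrower case here.
- *The toxicity endpoint has two conflicting SAE windows.* Those in section 7 are expedited-reporting rules, not analysis windows, and reporting to 90 days also satisfies the 30-day rule. Nor are late immune events shown to be lost: 1.1 and 5.6 follow them to 90 and about 100 days, and 7.8 sends all adverse events into routine data. What stands is the inconsistency for one recipient and the missing window for the tables.
- *Stating precision per arm is an error.* It is not. The figures reproduce and agree with 1.1, which has each cohort analysed separately. Section 13.9.2 says the same, but under the primary efficacy heading, so it does not clearly bar a pooled toxicity table.

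It is also fair to say that the numerical gap between the two interval rules is small, and that 90% or 95% is a matter of choice, since 13.1 reports progression-free and overall survival at 90%.

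**Conclusion.** The point holds as a set of inconsistencies to repair, with one improvement to add. The population wording has two readings, and one of them could drop a patient because of a toxicity; the number affected is probably very small and cannot be estimated from the documents. The ±20% in 13.1 does not describe the interval in 13.9.1. The planned interval would be about ±21% under assumed uniform or Jeffreys priors and ±23.3% if it became a 95% exact interval, and without a prior it is not reproducible. The toxicity tables lack a window, and the nearby reporting and follow-up periods disagree.

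Pooling is an improvement, not a correction. It rests on all 57 participants receiving one regimen and on toxicity rates being similar enough across histologies for a single rate to be meaningful. On that footing the maximum exact 95% half-width falls from 23.3% to 13.5%, and the chance of seeing at least one event with a true rate of 5% is 95% rather than 62%.

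**What to change.** 1. In 11.1, 11.1.1 and 13.9, define the toxicity population as participants with at least one dose of *eribulin or pembrolizumab*, so that these sections agree with 13.9.1.
2. Choose one interval method and level for toxicity, use it in both 13.1 and 13.9.1, and restate the precision to match. If the interval stays credible, give the prior.
3. Add a pooled toxicity summary over all treated participants and keep the per-cohort tables. The small downside is that pooling hides differences between cohorts, which the per-cohort tables still show.
4. Reconcile 7.3.2 with 7.6 and 7.7 on start, end and the new-therapy cut-off, and reconcile the immune follow-up in 1.1 and 5.6. Then state which window the toxicity tables use. A table window closed at 90 days would fall before the contact at about 100 days, so the choice should be explicit.

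The cost is protocol and SAP wording plus one extra table. Reporting of SAEs to 90 days is already required by 7.6 and 7.7, and no visits are added.

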13.9.1 Evaluation of Toxicity

Toxicity data will be summarized by frequency tables. For the toxicity endpoint, per-treated analysis will be used to include any participant who received the treatment regardless of the eligibility nor the duration or dose of the treatment received. Toxicity rate will be estimated with 95% credible interval.

13.9.2 Evaluation of the Primary Efficacy Endpoint

All analyses will be intent-to-treat analyses. All the analyses will be conducted separately by each cohort, leiomyosarcoma, liposarcoma, and undifferentiated pleomorphic sarcoma/other sarcomas.

13.9.3 Evaluation of Response

All eligible participants included in the study must be assessed for response to treatment, even if there are major protocol treatment deviations or if they are ineligible. Each participant will be assigned one of the following categories: 1) complete response, 2) partial response, 3) stable disease, 4) progressive disease, 5) early death from malignant disease, 6) early death from toxicity, 7) early death because of other cause, or 9) unknown (not assessable, insufficient data). [Note: By arbitrary convention, category 9 usually designates the “unknown” status of any type of data in a clinical database.] ^[1]_{SEP} All of the participants who met the eligibility criteria (with the possible exception of those who received no study medication) should be included in the main analysis of the response rate. Participants in response categories 4-9 should be considered to have a treatment failure (disease progression). Thus, an incorrect treatment schedule or drug administration does not result in exclusion from the analysis of the response rate. Precise definitions for categories 4-9 will be protocol specific. ^[1]_{SEP} All conclusions should be based on all eligible participants. Sub-analyses may then be performed on the basis of a subset of participants, excluding those for whom major protocol deviations have been identified (*e.g.*, early death due to other reasons, early discontinuation of treatment, major protocol violations, etc.). However, these sub-analyses may not serve as the basis for drawing conclusions concerning treatment

efficacy, and the reasons for excluding participants from the analysis should be clearly reported. The 95% confidence intervals should also be provided.

Statistical References:

1. Cox DR: Regression models and life tables (with discussion). J. R. Statistical Soc, B 34:187,220, 1972.
2. Kaplan EL, Meier P: Nonparametric estimator from incomplete observations. J. American Statistical Association 53:457-81, 1958.
3. Mantel N: Evaluation of survival data and two new rank order statistics arising in its consideration. Cancer Chemotherapy Reports 60:163-170, 1966.

14. PUBLICATION PLAN

The results should be made public within 24 months of reaching the end of the study. The end of the study is the time point at which the last data items are to be reported, or after the outcome data are sufficiently mature for analysis, as defined in the section on Sample Size, Accrual Rate and Study Duration. If a report is planned to be published in a peer-reviewed journal, then that initial release may be an abstract that meets the requirements of the International Committee of Medical Journal Editors. A full report of the outcomes should be made public no later than three (3) years after the end of the study.

16. APPENDIX A: PERFORMANCE STATUS CRITERIA

[figure not shown]
Table 11. Performance Status

ECOG Performance Status Scale		Karnofsky Performance Scale	
Grade	Descriptions	Percent	Description
0	Normal activity. Fully active, able to carry on all pre-disease performance without restriction.	100	Normal, no complaints, no evidence of disease.
		90	Able to carry on normal activity; minor signs or symptoms of disease.
1	Symptoms, but ambulatory. Restricted in physically strenuous activity, but ambulatory and able to carry out work of a light or sedentary nature (e.g. , light housework, office work).	80	Normal activity with effort; some signs or symptoms of disease.
		70	Cares for self, unable to carry on normal activity or to do active work.
2	In bed <50% of the time. Ambulatory and capable of all self-care, but unable to carry out any work activities. Up and about more than 50% of waking hours.	60	Requires occasional assistance, but is able to care for most of his/her needs.
		50	Requires considerable assistance and frequent medical care.
3	In bed >50% of the time. Capable of only limited self-care, confined to bed or chair more than 50% of waking hours.	40	Disabled, requires special care and assistance.
		30	Severely disabled, hospitalization indicated. Death not imminent.
4	100% bedridden. Completely disabled. Cannot carry on any self-care. Totally confined to bed or chair.	20	Very sick, hospitalization indicated. Death not imminent.
		10	Moribund, fatal processes progressing rapidly.
5	Dead.	0	Dead.

17. APPENDIX B: MANAGEMENT ALGORITHMS FOR ENDOCRINOPATHY, GASTROINTESTINAL, HEPATIC, NEUROLOGICAL, PULMONARY, RENAL, AND SKIN ADVERSE EVENTS

Endocrinopathy Management Algorithm

Rule out non-inflammatory causes. If non-inflammatory cause, treat accordingly and continue immuno-oncology (I-O) therapy. Consider visual field testing, endocrinology consultation, and imaging.

Patients on IV steroids may be switched to an equivalent dose of oral corticosteroids (e.g. prednisone) at start of tapering or earlier, once sustained clinical improvement is observed. Lower bioavailability of oral corticosteroids should be taken into account when switching to the equivalent dose of oral corticosteroids.

GI Adverse Event Management Algorithm

Rule out non-inflammatory causes. If non-inflammatory cause is identified, treat accordingly and continue I-O therapy. Opiates/narcotics may mask symptoms of perforation. Infliximab should not be used in cases of perforation or sepsis.

Grade of Diarrhea/ Colitis (NCI CTCAE v4)	Management	Follow-up
Grade 1 Diarrhea : < 4 stools/day over baseline; Colitis : asymptomatic	
 Continue I-O therapy per protocol Symptomatic treatment 	
 Close monitoring for worsening symptoms. Educate patient to report worsening immediately If worsens: Treat as Grade (G) 2 or 3/4
Grade 2 Diarrhea : 4-6 stools per day over baseline; IV fluids indicated <24 hours (hrs); not interfering with ADL Colitis : abdominal pain; blood in stool	
 Delay I-O therapy per protocol Symptomatic treatment 	
 If improves to grade 1: Resume I-O therapy per protocol If persists > 5-7 days or recurs: 0.5-1.0 mg/kg/day methylprednisolone or oral equivalent When symptoms improve to grade 1, taper steroids over at least 1 month, consider prophylactic antibiotics for opportunistic infections, and resume I-O therapy per protocol. If worsens or persists > 3-5 days with oral steroids: Treat as grade 3/4
Grade 3-4 Diarrhea (G3) : ≥7 stools per day over baseline; incontinence; IV fluids ≥24 hrs; interfering with activities of daily living (ADL) Colitis (G3) : severe abdominal pain, medical intervention indicated, peritoneal signs G4: life-threatening, perforation	
 Discontinue I-O therapy per protocol 1.0 to 2.0 mg/kg/day methylprednisolone IV or IV equivalent Add prophylactic antibiotics for opportunistic infections Consider lower endoscopy 	
 If improves: Continue steroids until grade 1, then taper over at least 1 month If persists > 3-5 days, or recurs after improvement: Add infliximab 5 mg/kg (if no contraindication). Note: Infliximab should not be used in cases of perforation or sepsis

Patients on IV steroids may be switched to an equivalent dose of oral corticosteroids (e.g. prednisone) at start of tapering or earlier, once sustained clinical improvement is observed. Lower bioavailability of oral corticosteroids should be taken into account when switching to the equivalent dose of oral corticosteroids.

Hepatic Adverse Event Management Algorithm

Rule out non-inflammatory causes. If non-inflammatory cause, treat accordingly and continue I-O therapy. Consider imaging for obstruction.

Grade of Liver Test Elevation (NCI CTCAE v4)	Management	Follow-up
Grade 1 AST or ALT > ULN to 3.0 x ULN and/or Total bilirubin (T. bili) > ULN - 1.5 x ULN	
 Continue I-O therapy per protocol 	
 Continue liver function tests (LFT) monitoring per protocol If worsens: Treat as Grade 2 or 3-4
Grade 2 AST or ALT > 3.0 to ≤ 5 x ULN and/or T. bili > 1.5 to ≤ 3 x ULN	
 Delay I-O therapy per protocol Increase frequency of monitoring to every 3 days 	
 If returns to baseline: Resume routine monitoring, resume I-O therapy per protocol If elevations persist > 5-7 days or worsen: 0.5-1 mg/kg/day methylprednisolone or oral equivalent and when LFT returns to grade 1 or baseline, taper steroids over at least 1 month, consider prophylactic antibiotics for opportunistic infections, and resume I-O therapy per protocol
Grade 3-4 AST or ALT > 5 x ULN and/or T.bili > 3 x ULN	
 Discontinue I-O therapy* Increase frequency of monitoring to every 1-2 days 1.0 to 2.0 mg/kg/day methylprednisolone IV or IV equivalent** Add prophylactic antibiotics for opportunistic infections Consult gastroenterologist 	
 If returns to grade 2: Taper steroids over at least 1 month If does not improve in >3-5 days, worsens or rebounds: Add mycophenolate mofetil 1 gram (g) twice daily (BID) If no response within an additional 3-5 days, consider other immunosuppressants per local guidelines

[figure not shown]
Patients on IV steroids may be switched to an equivalent dose of oral corticosteroids (e.g. prednisone) at start of tapering or earlier, once sustained clinical improvement is observed. Lower bioavailability of oral corticosteroids should be taken into account when switching to the equivalent dose of oral corticosteroids.

*I-O therapy may be delayed rather than discontinued if AST/ALT ≤ 8 x ULN and T.bili ≤ 5 x ULN.

**The recommended starting dose for grade 4 hepatitis is 2 mg/kg/day methylprednisolone IV.

Neurological Adverse Event Management Algorithm

[figure not shown]
Rule out non-inflammatory causes. If non-inflammatory cause, treat accordingly and continue I-O therapy.

Patients on IV steroids may be switched to an equivalent dose of oral corticosteroids (e.g. prednisone) at start of tapering or earlier, once sustained clinical improvement is observed. Lower bioavailability of oral corticosteroids should be taken into account when switching to the equivalent dose of oral corticosteroids.

Pulmonary Adverse Event Management Algorithm

[figure not shown]
Rule out non-inflammatory causes. If non-inflammatory cause, treat accordingly and continue I-O therapy. Evaluate with imaging and pulmonary consultation.

Patients on IV steroids may be switched to an equivalent dose of oral corticosteroids (e.g. prednisone) at start of tapering or earlier, once sustained clinical improvement is observed. Lower bioavailability of oral corticosteroids should be taken into account when switching to the equivalent dose of oral corticosteroids.

Renal Adverse Event Management Algorithm

[figure not shown]
Rule out non-inflammatory causes. If non-inflammatory cause, treat accordingly and continue I-O therapy

Patients on IV steroids may be switched to an equivalent dose of oral corticosteroids (e.g. prednisone) at start of tapering or earlier, once sustained clinical improvement is observed. Lower bioavailability of oral corticosteroids should be taken into account when switching to the equivalent dose of oral corticosteroids.

Skin Adverse Event Management Algorithm

Rule out non-inflammatory causes. If non-inflammatory cause, treat accordingly and continue I-O therapy.

Patients on IV steroids may be switched to an equivalent dose of oral corticosteroids (e.g. prednisone) at start of tapering or earlier, once sustained clinical improvement is observed. Lower bioavailability of oral corticosteroids should be taken into account when switching to the equivalent dose of oral corticosteroids.

*Refer to NCI CTCAE v4 for term-specific grading criteria.

